Study Title: Study of Time-restricted Eating on Weight Loss. A Randomized Controlled Trial of the Effects of Time-restricted Eating on Weight Loss in Obese Subjects.

NCT: 03393195

Date: May 14th, 2019

Experimental Design:

This is a pilot study to examine the metabolic effects of TRF in overweight/obese humans. 100+ overweight/obese (BMI>27, <43kg/m²) male and female subjects over the age of 18 will be recruited to participate in this study. Participants will receive an iHealth Bluetooth connected scale to use during the study. Participants will be randomized to one of two eating plans. 1) **8-hour eating window:** TRF group instructed to limit daily calorie intake between 12:00pm and 8:00pm each day (only water and black coffee/tea permitted outside of eating window); or 2) **Consistent meal timing:** participants are instructed to eat three structured meals each day during specified eating windows (7:00am-11:00am, 11:00am-3:00pm, 4:00pm-10:00pm) Group allocation will be provided to subjects using the Eureka mobile research platform, and no recommendation on total calorie or macronutrient intake was provided. Participants will be instructed to use their iHealth scales daily, preferably in the morning before their first meal (Table 1). The Eureka app will also send adherence surveys, sleep questionnaires, and food attitude surveys to participants throughout the study.

Participants who live within 60 miles of UCSF were invited to participate in in-depth metabolic testing at UCSF. Immediately prior to study start, participants will go to the Clinical and Translational Science Institute (CTSI) clinical research center at the University of California, San Francisco (UCSF) in order to collect baseline values for the measurements listed in Table 2. Since fasting glucose and insulin measurements will be collected, participants will be instructed to fast from 8:00pm the night before. Additionally, iPhone users will be given the option to use the Oura ring for sleep and activity tracking. After 12 weeks, participants will come to the CTSI clinic to repeat the baseline measurements.

Table 1. Measurements to be collected by subjects at home.

Measurement	Mode of Collection	Frequency
Weight	Bluetooth Scale	Daily
Adherence Survey	Eureka	Daily
Sleeping habits (PSQI)	Eureka	Monthly
Food Attitudes (RED Scale)	Eureka	Monthly

Table 2. Measurements to be acquired at baseline and 12-week follow-up (local subjects only)

Questionnaire: Age, Sex, Ethnicity, SES, BMI,
Physical Anthropometry: Waist Circumference, Waist-to-Hip-Ratio (WHR), Mid-thigh girth, bicep girth
DXA Direct Adiposity Measures: Fat mass (arms, legs, trunk, total), Lean mass (arms, legs, trunk, total), percent fat (arms, legs, trunk, total), Volumes (arms, legs, trunk, total), muscle mass (appendicular, total)
DXA Derived Adiposity Measures and Indices: Visceral Adipose Tissue (VAT), Subcutaneous Abdominal Adipose Tissue (SAT), Trunk fat to leg fat ratio, Trunk to leg volume ratio, fat mass index (FMI), fat-free mass index (FFMI)
DXA Bone Measures: Bone mass (arms, legs, lumbar spine, total), Bone Mineral Density (spine, total)
Biochemical and Hormonal Markers in Fasting Blood
Albumin, amylase, bilirubin, BUN, CO ₂ , CPK, creatinine, GGT, LDH, total protein, uric acid
Insulin Resistance & IGFs: glucose, insulin, HbA1C, BHBA
Lipid Profile & Lipid-soluble Micronutrients: TG, total cholesterol, HDLC, LDLC, Ca, Cl, Fe, K, Mg, Na, Phosphate,
Liver Enzymes: ALT, AST, ALK
Questionnaire-based Behaviors on Dietary Intake, Physical Activity, and Cognitive Eating
Dietary Intake (MEC Quantitative Food Frequency Questionnaire): nutrients, food items, food groups
Physical Activity (MEC Physical Activity Questionnaire): total METs, METs for moderate/vigorous activities
Cognitive/Psychological Eating Behaviors (Weight-Related Eating Questionnaire): scores for emotional eating, eating in response to external cues, eating with compensatory restraint (eating less before/after a big meal), eating with routine restraint (holding back at meals, counting calories, dieting)
Meal frequency and times
Weight cycling history and parental body shape information
Strength Isokinetics and Isometrics: peak torque, average peak torque, total work, average power, AGON/ANTAG ratio
Hangrip Strength
Doubly labeled water technique: Total energy expenditure
Resting Metabolic Rate

Statistical Analysis Plan:

The primary outcome will be percent change in weight since baseline, measured daily via iHealth, in the overall cohort of 100 participants. To estimate the intention-to-treat effect of treatment assignment, we will use a linear mixed model (LMM) with fixed effects for treatment assignment, days since baseline (as a continuous variable), and their interaction, and random effects for participant and day, with unstructured covariance matrix. The treatment effect will be estimated by the fixed effect for the treatment by day interaction, capturing the between-group divergence in weight loss trajectories. In sensitivity analyses, we will repeat the analysis after Winsorizing outliers, which will be defined as points more than 1.5 times the interquartile range below the 25th or above the 75th percentile of the overall distribution. No adjustment will be made to p-values or confidence intervals for multiple comparisons for the primary outcome.

Our secondary outcomes will include body fat, lean mass, fasting glucose, insulin, and HbA1c levels, resting metabolic rate, and total energy expenditure, assessed at the baseline and 12-week clinical visits for a subset of 46 participants. To estimate the intention to treat effect of treatment assignment on changes in these outcomes, we will use LMMs with fixed effects for treatment assignment, an indicator for the 12-week visit, and their interaction, and a random effects for participant. The treatment effect will be estimated by the interaction. In sensitivity analyses, we will repeat these analyses Winsorizing any outliers, defined as in the primary analysis. P-values and confidence intervals will be Bonferroni-corrected for 7 comparisons.

All other outcomes measured at the baseline and 12-week clinical visits will be considered exploratory and analyzed using the methods described for the secondary outcomes, without penalization for multiple comparisons.

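### Could the doubly labeled water baseline run into the assigned eating plan and dilute the total energy expenditure contrast?

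*Combined protocol and SAP*

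**What the plan says.** Under Experimental Design, local participants attend the research center to have the Table 2 baseline values taken: "Immediately prior to study start, participants will go to the Clinical and Translational Science Institute (CTSI) clinical research center". Follow-up is described as "After 12 weeks, participants will come to the CTSI clinic to repeat the baseline measurements". Assignment reaches participants through the app ("Group allocation will be provided to subjects using the Eureka mobile research platform"), with no day given.

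Table 2 names the method in a single line, "Doubly labeled water technique: Total energy expenditure". Table 1, the list of home measurements, contains weight, adherence, sleep and food attitudes, and no tracer samples.

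The Statistical Analysis Plan places total energy expenditure among seven secondary outcomes "assessed at the baseline and 12-week clinical visits for a subset of 46 participants". Each is analysed with a linear mixed model containing treatment, a 12-week indicator and their product. For the estimate it says: "The treatment effect will be estimated by the interaction".

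**The concern.** The other six secondary outcomes (body fat, lean mass, glucose, insulin, HbA1c, resting metabolic rate) can be obtained at a visit. Doubly labeled water cannot: it returns a mean over the days between dosing and the last sample, so a visit date alone does not say which days were measured.

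Suppose the tracer is given at the baseline visit and the plan begins straight afterwards. The baseline window then covers the first days on the assigned plan, and a follow-up window opening at the second visit covers days beyond week 12. No earlier contact for dosing is described, which makes this reading plausible. Because the model leaves the arm difference at baseline free, any plan effect inside the baseline window is removed in full from the estimated treatment effect. A null result for total energy expenditure might then reflect the timing of the measurement and not the absence of an effect.

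**Working it through.** **Inputs from the documents.** 46 participants; 12 weeks = 84 days; interaction estimand; correction for 7 comparisons. The plan gives no window length, effect size, SD or power for this outcome, so there is no stated figure to reproduce.

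**Assumptions.** Window W of 7 to 14 days; plan start s days after the tracer; onset of effect immediate, gradual (exponential with a 14-day constant) or linear over 84 days; 23 per arm; overall two-sided alpha 0.05.

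**Estimand.** Let D be the full between-arm effect on plan, f the mean share of D present in the baseline window and g the share present in the follow-up window. Then

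interaction = (arm difference at 12 weeks) − (arm difference at baseline) = D × (g − f).

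**Loss when the plan is still followed and the effect is level at follow-up (g = 1, or very nearly).**

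| Onset | Formula for f | W = 7 | W = 14 |
|---|---|---|---|
| Immediate, s = 0 | (W − s)/W | 7/7 = 100% | 14/14 = 100% |
| Immediate, s = 1 | (W − s)/W | 6/7 = 86% | 13/14 = 93% |
| Immediate, s = 7 | (W − s)/W | 0/7 = 0% | 7/14 = 50% |
| Gradual, s = 0 | 1 − (14/W)(1 − e^(−W/14)) | 21% | 37% |
| Linear over 84 days, s = 0 | ((W + 1)/2)/84 | 4/84 = 4.8% | 7.5/84 = 8.9% |
| Any, s ≥ W | 0 | 0% | 0% |

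An 8.9% loss leaves the information of 46 × 0.911² = 38 participants.

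**Power, gradual case.** Alpha per test is 0.05/7 = 0.00714. Setting D for 80% power with a clean baseline gives (2.690 + 0.842) × √(2/23) = 1.04 SD of change. With g = 0.998, power is Φ(3.532 × (g − f) − 2.690). For W = 7 this is Φ(3.532 × 0.785 − 2.690), about 53%; for W = 14 it is Φ(3.532 × 0.631 − 2.690), about 32%.

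**Cases that break the direction.**
- The effect is still rising linearly past day 84: (84 + (W + 1)/2)/84 − ((W + 1)/2)/84 = 1, so nothing is lost.
- The early effect has the opposite sign: f is negative, g − f exceeds g, and the bias is away from zero.
- The plan has stopped before a follow-up window that opens at week 12, with no carry-over: g = 0 and the interaction is −f × D, a change of sign.

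**What the text supports.** Overlap needs two things that are not written down: dosing at the visit and not before it, and a plan start before the last sample. Study start is not defined as the first day on plan. The only stated purpose of the visit is to obtain baseline values, which points toward a measurement finished beforehand. The missing tracer samples in Table 1 do not decide the matter: they count as much against a window that opens at the visit and continues at home as against one that opens earlier.

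**The case for a change.** The strongest case for acting is that the omission is real and concerns an outcome that is formally tested. A visit date does not define this measurement, the model offers no protection against a contaminated baseline, and in the immediate-onset case a one-day lag already costs 86% to 93% of the contrast. Writing down a few dates seems a small price, and if collection is over the change is wording only.

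The omission stands, and so does the mechanism. The step to a change does not.

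- The document gives no operating procedure for any Table 2 measurement, so silence on tracer days is weak evidence that they were badly chosen.
- If dosing, sampling and plan-start dates were recorded, they would settle whether overlap occurred. A null result would not be beyond interpretation.
- Holding back the plan for an assumed 7 to 14 days after the visit would move the other six secondary baselines away from the start of the plan unless they were repeated. It would give local and remote participants different lead-ins and force a redefinition of day 0 in the primary weight model, which the concern otherwise leaves alone.
- Ending the follow-up window at week 12 would need an extra contact or home sampling.
- Parts of the design text are in the past tense and the subset is given as exactly 46, which suggests that local enrolment may already have taken place.

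**Conclusion.** The timing of the tracer windows relative to the plan is not stated, and overlap would bias the total energy expenditure interaction. Overlap itself is not established. Its effect could be anything from 0% to 100% of the contrast, because window length, start lag and onset are all assumptions. A bias toward zero further requires that participants are still on plan at follow-up, that the effect has levelled off, and that the early and week-12 effects share a sign.

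This is missing operational detail that investigators running a multi-day tracer study would probably settle sensibly. It touches one of seven secondary outcomes in a subset of a self-described pilot, and it does not alter how the primary weight outcome is analysed. The operational remedy is neither cheap nor clearly better. The trial report should give the actual window dates and, if the windows did overlap the plan, should not present the contrast as a clean before-and-after effect. That is a matter of reporting, and the plan can stand.

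### The primary intention-to-treat slope rests on home weighing alone, with no instruction to keep weighing after stopping the eating plan and no check on departures from missing at random

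*Combined protocol and SAP*

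**What the plan says.** **Source of the primary data.** The Statistical Analysis Plan takes the primary outcome from iHealth readings: "The primary outcome will be percent change in weight since baseline, measured daily via iHealth, in the overall cohort of 100 participants". Under Experimental Design, "Participants will be instructed to use their iHealth scales daily, preferably in the morning before their first meal (Table 1"). That instruction does not depend on following the eating plan, but it does not mention weighing after the plan is stopped either.

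**Model.** The primary analysis is a linear mixed model with "fixed effects for treatment assignment, days since baseline (as a continuous variable), and their interaction, and random effects for participant and day". Its arm-by-day interaction is the treatment effect and is described as intention-to-treat. No missing-data assumption is stated.

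**Sensitivity analysis.** "In sensitivity analyses, we will repeat the analysis after Winsorizing outliers" is the only one planned for the primary outcome.

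**Week-12 clinic data.** "After 12 weeks, participants will come to the CTSI clinic to repeat the baseline measurements", but Table 2 restricts these measurements to local participants, and the secondary outcomes are "assessed at the baseline and 12-week clinical visits for a subset of 46 participants". Clinic measurements feed the secondary and exploratory analyses, not the primary one.

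**Adherence.** Table 1 lists a daily adherence survey. No planned analysis uses it to examine missing weights.

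**The concern.** Suppose a participant follows the plan for four weeks, loses weight, then gives up both the plan and the scale and drifts back. The primary data hold only the four good weeks. A likelihood-based mixed model handles the missing eight as though that person's weight had continued on a line between their own early slope and the arm's average slope. That is sound only if weight after stopping evolves as it does in continuing participants with the same history. When people regain, or merely level off, after stopping, the fitted slope describes an arm in which everyone continued. An intention-to-treat effect would include the regain.

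This is separate from curvature: it remains if every observed trajectory is perfectly straight.

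Participants know their assignment, and the plans make different demands. One allows no calories before noon; the other asks for three meals in set windows. Unequal stopping is therefore plausible in either direction. Winsorizing changes extreme readings that were observed and is silent about readings that were not.

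**Working it through.** **Inputs from the documents.** Primary cohort 100 (Experimental Design says 100 or more), clinic subset 46, follow-up 12 weeks (84 days). The documents contain no dropout, regain, effect-size or variance figure, so there is no planned calculation to reproduce. Every input below is an assumption.

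**Step 1: coverage of the clinic visit.** 100 - 46 = 54 participants have no planned clinic visit at week 12. For them, home readings are the only end-of-study weights. For the other 46, clinic measurements exist but do not enter the primary model.

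**Step 2: closed form at week 12.** Let m be the on-plan percent change by week 12 (negative for loss), p the proportion who stop plan and scale, and f the fraction of m that stoppers have failed to keep by week 12 (f = 1 is full return to baseline). T is TRF and C is control.

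- Planned model: m_T - m_C
- All follow-up observed: m_T(1 - f p_T) - m_C(1 - f p_C)
- Bias = planned minus all-follow-up = f(p_T m_T - p_C m_C)

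Example, 30% against 10% stopping, 2% loss in both arms, f = 1: (0.30)(-2) - (0.10)(-2) = -0.60 + 0.20 = -0.40. At f = 0.5 this is -0.20.

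Example, equal 20% stopping, loss 3% against 2%, f = 1: -0.60 + 0.40 = -0.20. At f = 0.5 this is -0.10.

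**Step 3: simulation.** A random-intercept, random-slope model was fitted to readings cut at stopping and compared with the same model fitted to full follow-up. For the 25%/10%, 15%/10% and 3%/3% rows: 50 per arm, 70% of days weighed, slope SD 3 percentage points (pp) over 12 weeks, stopping between days 14 and 42, 150 replicates. For the other rows with equal 2% loss: 800 per arm, slope SD 2.5 pp, stopping between days 14 and 56, one fit each with standard error 0.13 to 0.14. Stoppers return to baseline by day 84. Ranges are across repeated runs or, for 15%/10%, across the loss values.

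| Stopping T / C | On-plan loss T / C | Closed form, f = 1 (pp) | Simulated bias (pp) |
|---|---|---|---|
| 20% / 20% | 2% / 2% | 0 | about 0 |
| 15% / 10% | 1.5-2% in both | -0.08 to -0.10 | -0.05 to -0.12 |
| 25% / 10% | 2% / 2% | -0.30 | -0.31 to -0.35 |
| 30% / 10% | 2% / 2% | -0.40 | -0.46 |
| 30% / 10% | 3% / 3% | -0.60 | -0.65 to -0.70 |
| 40% / 10% | 2% / 2% | -0.60 | -0.69 |
| 10% / 30% | 2% / 2% | +0.40 | +0.49 |
| 20% / 20% | 3% / 2% | -0.20 | -0.21 to -0.24 |
| 30% / 10% | 3% / 2% | -0.70 | not simulated |
| 40% / 10% | 3% / 2% | -1.00 | not simulated |

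Negative values favour TRF. At 50 per arm the standard error of the effect is about 0.62 pp, so -0.31 is 0.31/0.62 = 0.5 standard errors and -0.70 is 0.70/0.62 = 1.1.

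**Step 4: value of a final weight.** In the 25%/10%, 2% scenario, a day-84 reading from 70% of stoppers reduces the bias to between -0.12 and -0.16 pp. A reading from all stoppers reduces it to between -0.06 and -0.09 pp.

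**The case against.** The strongest reply is that a likelihood-based mixed model under missing at random is a standard primary analysis, and that daily weighing already schedules a home reading at week 12 for everyone. Anyone who stops the plan but keeps weighing stays in the data and causes no such bias. All of this stands. The concern is therefore conditional: it needs people to stop the scale as well as the plan, and their weight then to leave the trend. The documents neither show nor exclude that.

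Several stronger readings are tempting and are not supported:

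- **Stopping the plan means stopping the scale because both run through one app.** Table 1 lists weight under the Bluetooth scale and the surveys under Eureka. No link between the two is described.
- **The model carries the last observation forward.** It projects a slope that blends the participant's own data with the arm's.
- **Only unequal stopping matters.** The equal-stopping rows with 3% against 2% loss show otherwise.
- **The trial would report a false TRF benefit.** With equal on-plan loss and more stopping under TRF, the planned estimate centres near zero (-0.03 at 30%/10%) while full follow-up gives +0.43. It would hide a disadvantage rather than create a benefit. If the control arm stops more, the sign reverses.
- **Nothing planned could reveal the problem.** Body fat, lean mass and the other 12-week clinic measurements, including BMI, are compared by arm without relying on home weighing. This is a real but partial check: it covers 46 of 100, all local, and BMI is listed under the questionnaire.

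It is also fair that the study calls itself a pilot and that the size rests wholly on assumptions. Neither removes the gap, because the plan still claims an intention-to-treat effect from a randomized comparison.

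**Conclusion.** The point holds in conditional form. The plan leaves the primary effect exposed to weights that are missing because participants gave up, and has no primary analysis that would measure that exposure. Size and direction cannot be known from the documents. Under the assumed inputs, with at least as much stopping in the TRF arm, the bias is about -0.1 to -0.7 pp over 12 weeks. It reaches -1.0 pp only in the most extreme row and has the opposite sign when the control arm stops more. It is near zero when stopping and on-plan loss are both equal. Set against a standard error of about 0.6 pp, the middle of that range could change how the result is read, and the lower end would not. These figures assume that stoppers also cease weighing and are mostly back at baseline by week 12; less regain gives less bias. This is a worthwhile, cheap improvement and does not show that the planned model is invalid.

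**What to change.** 1. **Collection.** For participants still in follow-up, state that daily weighing continues whatever their adherence to the eating plan. Send everyone, including those who have stopped, an Eureka-prompted weigh-in with reminders in a fixed window around day 84, and include those readings in the primary model. Experimental Design describes some steps in the past tense, so this may come too late for some participants; the analysis changes below do not depend on it.

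2. **Analysis.** State the missing-at-random assumption in the Statistical Analysis Plan. Report by arm how many participants have no reading in the last two weeks. Add one pattern-mixture sensitivity analysis for them, with return to baseline as one scenario and a range of arm-specific shifts extended until the conclusion changes.

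3. **Local subset.** A comparison of week-12 DXA mass between those still weighing and those who stopped can be shown descriptively only. With 23 per arm assumed and stopping of 25% and 10%, about 23 x 0.25 + 23 x 0.10 = 8 stoppers would be expected among the 46.

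**Cost.** One app prompt and one paragraph of the analysis plan, with no added visits, staff or participants. The drawbacks are some reminder burden and a sensitivity estimate that will be wider and probably less favourable.

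### The primary slope model has no baseline covariates; pre-specifying baseline weight and local residence, each interacted with day, is a cheap improvement with a modest, uncertain gain in precision

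*Combined protocol and SAP*

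**What the plan says.** In the Statistical Analysis Plan section, the outcome is set out as follows: "The primary outcome will be percent change in weight since baseline, measured daily via iHealth, in the overall cohort of 100 participants". The fixed part of the linear mixed model has "fixed effects for treatment assignment, days since baseline (as a continuous variable), and their interaction". The random part is "random effects for participant and day, with unstructured covariance matrix", which I read as a random intercept and a random slope per person. The estimand is a difference in slopes: "The treatment effect will be estimated by the fixed effect for the treatment by day interaction". The only sensitivity analysis for the primary outcome is Winsorizing.

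The Experimental Design section describes randomisation to two eating plans. It states no allocation ratio and no stratification factors. It also shows which baseline variables could be used:

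- **Baseline weight** must exist for every analysed participant, because it is the denominator of the outcome.
- **Local residence** must be known, because it decided who was asked to attend: "Participants who live within 60 miles of UCSF were invited to participate in in-depth metabolic testing at UCSF".
- **Sex** appears in Table 2 ("Questionnaire: Age, Sex, Ethnicity, SES, BMI"), but the heading of that table limits it to local participants. Table 1, the home measurements, does not list it.

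**The concern.** With daily weights over 12 weeks, each person's own slope is estimated closely. Most of the uncertainty in the treatment-by-day term then comes from how much slopes differ between people in the same arm. The planned model has no term that explains any of that variation. If baseline weight or local residence predicts the rate of percent loss, that predictable part stays in the error and widens the confidence interval. Chance imbalance between arms in such a factor adds to the same error, and no stratification is described that would limit it.

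What is at stake is efficiency: the width of the primary interval in a study of about 100 people that calls itself a pilot. The validity of the comparison is not in question.

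**Working it through.** **Inputs from the documents.** N = 100 ("in the overall cohort of 100 participants"; the recruitment target is "100+ overweight/obese (BMI>27, <43kg/m²) male and female subjects over the age of 18 will be recruited"). There are two arms, 12 weeks of daily weights, and 46 participants in the clinic subset. The documents give no power, effect size, SD, alpha or R², so there is no planned figure to reproduce.

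**Assumptions.** 1:1 allocation (50 per arm). R² is the share of between-person slope variance that the covariates explain, taken as 0 to 0.20. For the simulation check: SD of the 12-week slope 3 percentage points, residual SD 0.8, intercept SD 0.5 to 0.8.

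**Step 1: does between-person spread dominate?** The between-person part of the SE is 3 × sqrt(4/100) = 0.600. The SE of the planned model in the simulation (84 daily weights, variance components treated as known) was 0.603. The between-person share of the variance is 0.600²/0.603² = 0.3600/0.3636 = 0.99. Under these assumptions nearly all the variance is of the kind that covariates could explain.

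**Step 2: main effects alone.** A covariate main effect shifts a person's level and leaves the slope alone. In the simulation, adding main effects only gave an identical treatment-by-day estimate and the same SE (0.603 against 0.603) with complete data. With about 20% early dropout plus 20% missed days the SE ratio was 1.001. Only covariate-by-day terms can help.

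**Step 3: two covariates, each interacted with day.** Explaining a share R² of slope variance multiplies the variance by (1 − R²). Chance correlation of q covariates with arm multiplies it by about (N − 3)/(N − 3 − q), which is 97/95 for N = 100 and q = 2. So the SE ratio is sqrt((1 − R²) × 97/95), and the equivalent N is 1/(SE ratio)².

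| Assumed R² | (1 − R²) × 97/95 | SE ratio | Change in SE | Equivalent change in N |
|---|---|---|---|---|
| 0 | 1.021 | 1.010 | +1.0% | −2.1% |
| 0.05 | 0.970 | 0.985 | −1.5% | +3.1% |
| 0.10 | 0.919 | 0.959 | −4.1% | +8.8% |
| 0.20 | 0.817 | 0.904 | −9.6% | +22.4% |

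Break-even: R² = 1 − 95/97 = 2/97 = 0.021.

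**Step 4: check of the formula.** The simulation used three covariates, for which the factor is 97/94. The formula gives 1.016, 0.990, 0.964 and 0.909 at R² = 0, 0.05, 0.10 and 0.20. The simulation gave 1.017, 0.991, 0.965 and 0.911. The three-covariate break-even is 3/97 = 0.031. The two-covariate case was not simulated; it rests on the same formula.

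**Step 5: how large could chance imbalance be?** If 46% of participants were local (an assumption: 46 is the number assessed in clinic, and the number living within 60 miles is not given), the SD of the between-arm difference in local share is sqrt(0.46 × 0.54 × (1/50 + 1/50)) = sqrt(0.00994) = 0.10, or 10 percentage points.

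**The case against.** The strongest case for leaving the plan alone is that it contains no error. A pre-specified unadjusted model is a legitimate and simple choice for a pilot, and it avoids argument over which covariates to include. Nothing in the documents links baseline weight or residence to the rate of percent loss. At the low end of the assumed range the gain is 1.5% of an SE. All of that stands, and it is why this is only an optional improvement.

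A reader might also infer stronger claims that the documents do not support:

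- **That the result is biased, or that chance imbalance is a separate defect.** Under randomisation the unadjusted slope difference is unbiased, and its interval already reflects chance imbalance.
- **That baseline weight is ignored.** It is the denominator of the outcome and is absent only as a covariate. Whether it still predicts the rate of percent loss is unknown.
- **That sex is already in hand for everyone.** Admitting both sexes does not show that sex is recorded for remote participants. If it were held only for the 46 in the clinic subset, a model with sex would have to drop or impute the other 54 of 100.
- **That adjustment costs nothing.** Below about 2% explained variance the SE rises.
- **That clinic attendance should be the covariate because it brings more contact.** Living within 60 miles led to an invitation, and not everyone invited need have attended. The documents do not say when allocation was revealed relative to the baseline visit, so only residence is clearly fixed before randomisation.

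**Conclusion.** The point holds as a cheap improvement. The primary model explains none of the within-arm spread in slopes, so precision may be lost. How much, if any, depends on an R² that the documents do not give. Over an assumed 5% to 20%, adjustment for two covariates lowers the SE by about 1.5% to 10%; at worst it raises it by about 1%. This rests on 1:1 allocation, 100 analysed participants, slope variation that dominates daily measurement error, and covariates entered with day interactions.

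**What to change.** Add one sentence to the primary analysis in the Statistical Analysis Plan: the mixed model also includes centred baseline weight and local residence (within 60 miles, as known before randomisation, not clinic attendance), each as a main effect and as an interaction with day. Add sex in the same form only after confirming that it is recorded for all participants. Keep treatment-by-day as the treatment effect, and report the planned unadjusted model as a sensitivity analysis. Fix the covariate list before outcome data are examined.

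The cost is one sentence and no new data collection for the two named covariates, with a possible SE increase of about 1% if neither predicts slope. With sex as a third covariate the worst case becomes about 1.6% and break-even about 3%.
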